9.3 Liver safety monitoring

To ensure subject safety and enhance reliability in determining the hepatotoxic potential of an investigational drug, a standardized process for identification, monitoring and evaluation of liver events has to be followed.

Please refer to Table 15-1 in Appendix 1 for complete definitions of liver events.

Follow-up of liver events

Every liver event defined in Table 15-1 of Appendix 1 should be followed up by the investigator or designated personnel at the trial site, as summarized below. Additional details on actions required in case of liver events are outlined in Table 15-2 of Appendix 1.

- Repeating liver chemistry tests (ALT, AST, TBL, PT/INR, ALP and γGT) to confirm elevation within 48-72 hours.
 - These liver chemistry repeats should always be performed using the central laboratory, with the results provided via the standard electronic transfer. If results will not be available from the central laboratory within 24 hours, then the repeats can also be performed at a local laboratory to monitor the safety of the subject. If a liver event is subsequently reported, any local liver chemistry tests previously conducted that are associated with this event should have results reported on the unscheduled local laboratory CRF.
 - If the initial elevation is confirmed, close observation of the subject will be initiated, including consideration of treatment interruption if deemed appropriate.
- Discontinuation of the investigational drug (refer to Section 7.2 (Discontinuation of study treatment), if appropriate
- Hospitalization of the subject if appropriate
- Causality assessment of the liver event
- Thorough follow-up of the liver event should include:
 - Repeating liver chemistry tests two or three times weekly. Testing should include ALT, AST, ALP, PT/INR, and gGT. If total bilirubin is elevated > 2 x ULN, fractionation into direct and indirect bilirubin is required. To rule out muscular origin of transaminase elevations, CPK should be measured along with liver chemistry tests. Frequency of retesting can decrease to once a week or less if abnormalities stabilize or the study drug has been discontinued and the subject is asymptomatic. Retesting should be continued up to resolution.
 - Obtaining a more detailed history of symptoms and prior or concurrent diseases.
 - Obtaining a history of concomitant drug use (including nonprescription medications and herbal and dietary supplement preparations), alcohol use, recreational drug use, and special diets.
 - Exclusion of underlying liver disease, as specified in Table 15-3.
 - Imaging such as abdominal US, CT or MRI, as appropriate
 - Obtaining a history of exposure to environmental chemical agents.
 - Considering gastroenterology or hepatology consultations.

All follow-up information, and the procedures performed must be recorded as appropriate in the CRF.

9.4 Renal safety monitoring

Every renal laboratory trigger or renal event must be followed up by the investigator or designated personnel at the trial site. Recommended follow-up assessments are listed in Section 16 (Appendix 2).

9.5 Reporting Medication errors including misuse/abuse

Medication errors are unintentional errors in the prescribing, dispensing, administration or monitoring of a medicine while under the control of a healthcare professional, patient/subject or consumer (EMA definition).

Misuse refers to situations where the medicinal product is intentionally and inappropriately used not in accordance with the protocol.

Abuse corresponds to the persistent or sporadic, intentional excessive use of a medicinal product, which is accompanied by harmful physical or psychological effects.

All study treatment errors and uses outside of what is foreseen in the protocol will be collected in the dose administration record (DAR) CRF. Study treatment errors are only to be reported to Novartis Drug Safety and Epidemiology department if the treatment error is associated with an SAE.

All instances of misuse or abuse must be documented in the adverse event (AE) CRF irrespective of the misuse/abuse being associated with an AE/SAE. In addition, all instances of misuse or abuse must be reported to Novartis Drug Safety and Epidemiology. As such, instances of misuse or abuse are also to be reported using the SAE form/CRF. Table 9-1 summarizes the reporting requirements.

 Table 9-1
 Summary of reporting requirements for medication errors

Treatment error type	Document in Dose Administration (DAR) CRF	Document in AE CRF	Complete SAE form/CRF
Unintentional study treatment error	Yes	Only if associated with an AE	Only if associated with an SAE
Misuse/Abuse	Yes	Yes	Yes, even if not associated with a SAE

For more information on AE and SAE definition and reporting requirements, please see Section 9.1 and Section 9.2, respectively.

9.6 Pregnancy reporting

To ensure subject safety, each pregnancy occurring after signing the informed consent must be **reported to Novartis within 24 hours** of learning of its occurrence. The pregnancy should be followed up to determine outcome, including spontaneous or voluntary termination, details of the birth, and the presence or absence of any birth defects, congenital abnormalities, or maternal and/or newborn complications.

Pregnancy must be recorded on the Pharmacovigilance Pregnancy Form and reported by the investigator to the local Novartis Drug Safety and Epidemiology Department. Pregnancy follow-up should be recorded on the same form and should include an assessment of the possible relationship to the study treatment.

Any SAE experienced during the pregnancy and unrelated to the pregnancy must be reported on a SAE form.

The study drug must be discontinued, though the subject may stay in the study, if she wishes to do so. All assessments that are considered as a risk during pregnancy must not be performed. The subject may continue all other protocol assessments.

Pregnancy outcomes should be collected for the female partners of any males who took study treatment in this study. Consent to report information regarding these pregnancy outcomes should be obtained from the mother.

9.7 Early phase safety monitoring

The Investigator will monitor adverse events in an ongoing manner and inform the Sponsor of any clinically relevant observations. Any required safety reviews will be made jointly between medically qualified personnel representing the Sponsor and Investigator. Such evaluations may occur verbally, but the outcome and key discussion points will be summarized in writing (e-mail) and made available to both Sponsor and all Investigator(s). Criteria pertaining to stopping the study/treatment or adapting the study design are presented above.

When two or more clinical site(s) are participating in the clinical study, the Sponsor will advise the Investigator(s) at all sites in writing (e-mail) (and by telephone if possible) of any new, clinically relevant safety information reported from another site during the conduct of the study in a timely manner.

10 Data review and database management

10.1 Site monitoring

Before study initiation, at a site initiation visit or at an investigator's meeting, a Novartis representative will review the protocol and CRFs with the investigators and their staff. During the study Novartis employs several methods of ensuring protocol and GCP compliance and the quality/integrity of the sites' data. The monitor will visit the site to check the completeness of subject records, the accuracy of entries on the CRFs, the adherence to the protocol and to Good Clinical Practice, the progress of enrollment, and ensure that study drug is being stored, dispensed, and accounted for according to specifications. Key study personnel must be available to assist the monitor during these visits.

The investigator must maintain source documents for each subject in the study, consisting of case and visit notes (hospital or clinic medical records) containing demographic and medical information, laboratory data, electrocardiograms, and the results of any other tests or assessments. All information on CRFs must be traceable to these source documents in the subject's file. The investigator must also keep the original informed consent form signed by the subject (a signed copy is given to the subject).

The investigator must give the monitor access to all relevant source documents to confirm their consistency with the CRF entries. Novartis monitoring standards require full verification for the presence of informed consent, adherence to the eligibility criteria, documentation of SAEs, and the recording of data that will be used for all primary and safety variables. Additional checks of the consistency of the source data with the CRFs are performed according to the study-specific monitoring plan. No information in source documents about the identity of the subjects will be disclosed.

10.2 Data collection

Designated investigator staff will enter the data required by the protocol into the Electronic Case Report Forms using fully validated software that conforms to 21 CFR Part 11 requirements. Designated investigator site staff will not be given access to the EDC system until they have been trained. Automatic validation programs check for data discrepancies and, by generating appropriate error messages, allow the data to be confirmed or corrected before transfer of the data to ClinBAY. The Investigator must certify that the data entered into the Electronic Case Report Forms are complete and accurate. After database lock, the investigator will receive copies of the subject data for archiving at the investigational site.

Data not requiring a separate written record will be defined in the Site Operations Manual and Assessment schedule and can be recorded directly on the CRFs. All other data captured for this study will have an external originating source (either written or electronic) with the CRF not being considered as source.

All data should be recorded, handled and stored in a way that allows its accurate reporting, interpretation and verification.

10.3 Database management and quality control

Novartis staff or CRO working on behalf of Novartis review the data entered into the CRFs by investigational staff for completeness and accuracy and instruct the site personnel to make any required corrections or additions. Queries are sent to the investigational site using an electronic data query. Designated investigator site staff is required to respond to the query and confirm or correct the data. If the electronic query system is not used, a paper Data Query Form will be faxed to the site. Site personnel will complete and sign the faxed copy and fax it back to Novartis staff or CRO working on behalf of Novartis who will make the correction to the database. The signed copy of the Data Query Form is kept at the investigator site.

Concomitant medications entered into the database will be coded using the WHO Drug Reference List, which employs the Anatomical Therapeutic Chemical classification system. Medical history/current medical conditions and adverse events will be coded using the Medical dictionary for regulatory activities (MedDRA) terminology.

Laboratory samples will be processed centrally and the results will be sent electronically to Novartis (or a designated CRO).

Diary data will be entered into an electronic diary by the subject. The system will be supplied by a vendor(s), who will also manage the database. The database will be sent electronically to Novartis (or a designated CRO).

Randomization codes and data about all study drug(s) dispensed to the subject and all dosage changes will be tracked using an Interactive Response Technology (IRT). The system will be supplied by a vendor, who will also manage the database. The database will be sent electronically to Novartis (or a designated CRO).

Each occurrence of a code break via IRT will be reported to the clinical team and monitor. The code break functionality will remain available until study shut down or upon request of Novartis.

The occurrence of any protocol deviations will be determined. After these actions have been completed and the database has been declared to be complete and accurate, it will be locked and the treatment codes will be unblinded and made available for data analysis. Any changes to the database after that time can only be made by joint written agreement between the COAR Analytics NIBR Franchise Head and the relevant NIBR TA Head.

Company Confidential Information

10.4 Data Monitoring Committee

Not required.

10.5 Adjudication Committee

Not required.

11 Data analysis

The analyses will be conducted on all subject data at the time the trial ends.

11.1 Analysis sets

For all analysis sets, subjects will be analyzed according to the study treatment(s) received.

The safety analysis set will include all subjects that received any study drug.

Company Confidential Information

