Title	A randomized, subject- and investigator-blinded, placebo-controlled, multi-center, multiple dose study to assess the efficacy and safety of CJM112 in patients with inadequately controlled moderate to severe asthma		
Brief title	Study of safety and efficacy of CJM112 in moderate to severe asthmatics		
Sponsor and Clinical Trial Phase	Novartis Phase II		
Intervention type	Biologic		
Study type	Interventional		
An unmet medical need exists for patients with moderate and severe as who continue to demonstrate symptoms despite being on standard of medications, and are not eligible for other biologic therapies developed development for T2-high (allergic/eosinophilic) asthma (such as omaliz and mepolizumab) because they have low circulating IgE and eosinophil at baseline. The purpose of this study is to determine if CJM112, an anti-Il antibody, when added to existing therapy, displays the clinical efficacy safety profile to support further development in patients with inadequence controlled moderate to severe asthma with low IgE and low circulating IgE and low circulating IgE and I			
Primary Objective(s)	To determine whether treatment with CJM112 in patients with inadequately controlled moderate to severe asthma leads to an improvement in airflow obstruction as reflected by change from baseline in FEV1 in mL.		
Secondary Objectives	To determine whether treatment with CJM112 in patients with inadequately controlled moderate to severe asthma: 1. leads to an improvement in FEV1% of predicted. 2. leads to an improvement in asthma control as reflected by change from baseline in ACQ score 3. is safe and well tolerated by evaluating study treatment discontinuations and adverse events		
Study design	12 week, non-confirmatory, randomized, subject- and investigator-blinded, placebo-controlled, multi-center, parallel-arm study in which patients will be randomized 3:2 to CJM112:placebo.		
Population	The study population will consist of approximately 110 male and female patients between 18 and 75 years old with uncontrolled symptoms of moderate or severe asthma (defined by ACQ score of ≥1.5) who are compliant on standard of care medications.		

	1. Patients with a physician-diagnosed history of moderate to severe asthma for a period of at least one year prior to screening.		

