1.4 Study purpose

The purpose of this study is to determine whether CJM112, when added to existing therapy, displays the clinical efficacy and safety profile to support further development in patients with inadequately controlled moderate to severe asthma.

Study objectives and endpoints 2

2.1 **Primary objective(s)**

Primary objective(s)	Endpoints related to primary objective(s)	
To determine whether treatment with CJM112 in patients with inadequately controlled moderate to severe asthma leads to an	Change from baseline FEV1 in mL	
improvement in airflow obstruction		

Secondary objective(s) 2.2

Secondary objective(s)	Endpoints related to secondary objective(s)	
To determine whether treatment with CJM112 in patients with inadequately controlled moderate to severe asthma leads to an improvement in FEV1% of predicted	 Change from baseline FEV1 % of predicted 	
• To determine whether treatment with CJM112 in patients with inadequately controlled moderate to severe asthma leads to an improvement in asthma control	• Change from baseline in ACQ score, % of patients with ≥ 0.5 decrease in ACQ score	
To assess the safety and tolerability of CJM112 in patients with inadequately controlled moderate to severe asthma	Study treatment discontinuations and adverse events	

2.3 **Exploratory objective(s)**

3 Investigational plan

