3.1 Study design

This is a non-confirmatory, randomized, subject- and investigator-blinded, placebo-controlled, multi-center, parallel-arm study evaluating the efficacy of CJM112 on top of standard of care in patients with inadequately controlled moderate to severe asthma. This study will enroll approximately 110 patients. After an initial screening visit and run-in period of approximately 4 weeks, subjects eligible per inclusion and exclusion criteria at the baseline visit will be randomized (3:2) to receive Company Confidential Information CJM112 or matching placebo subcutaneously over 3 months during visits at the clinical study site. All baseline safety evaluation results must be available prior to the first dose. After the end of the treatment period, subjects will be followed for an additional 13 weeks. Site visits to administer dose and assess safety and efficacy will be scheduled as depicted in the figure below.

Figure 3-1 Study Design

Company Confidential Information

Screening and Run-In: Patients will provide informed consent and participate in an initial screening visit consisting of vital signs, physical exam, blood chemistry, ECG, pulmonary function tests, and ACQ. Subjects who meet all eligibility criteria at the screening visit will be dispensed a daily symptom diary and be asked to perform peak flow measurements over the approximately 4 week run-in period until the baseline visit.

Baseline: Subjects who qualify based on screening and run-in assessments will return for a baseline evaluation between Day -5 to Day -2. Subjects who meet all the applicable inclusion/exclusion criteria at screening and baseline will be randomized and will enter the treatment period. All screening and baseline assessments results must be available prior to randomization.

Treatment Period:

Company Confidential Information

At treatment period visits, safety, Company Confidential Information assessments will be performed. Safety assessments will include physical examinations, open ended health inquiry, ECGs, vital signs, standard clinical laboratory evaluations (hematology, blood chemistry, urinalysis), AEs and SAE monitoring.

Company Confidential Information

Company

Safety Follow-up: After completing the last dose Confidential Information, subjects will enter an additional follow-up period consisting of a visit on Day 92, Day 134 and an End of Study (EOS) visit on Day 176.

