# 2 First interpretable results (FIR)

# 3 Interim analyses

## 4 Statistical methods: Analysis sets

For subjects for which the actual treatment received does not match the randomized treatment the treatment actually received will be used for the analysis.

The safety analysis set will include all subjects that received any study drug.

The PK analysis set will include all subjects with at least one available valid (i.e. not flagged for exclusion) PK concentration measurement, who received any study drug and experienced no protocol deviations with relevant impact on PK data.

The PD analysis set will include all subjects with any available PD data and experienced no protocol deviations with relevant impact on PD or efficacy data. If a subject has an asthma exacerbation adverse event during the study, all subsequent efficacy assessments will be excluded from the PD analysis set.

The analysis sets and protocol deviation codes are related as follows:

Table 4-1 Protocol deviation codes and analysis sets

Category Deviation code	Text description of deviation	Data exclusion	
Subjects are exclude	ded from PD analysis in case of these PDs:	Exclude subject from PD analysis set	
INCL05	Deviation from inclusion criterion 5	Yes	
INCL07	Deviation from inclusion criterion 7	Yes	
EXCL01	Deviation from exclusion criterion 1	Yes	

Page 16

CJM112X2204

Category Deviation code	Text description of deviation	Data exclusion
EXCL02	Deviation from exclusion criterion 2	Yes
EXCL03	Deviation from exclusion criterion 3	Yes
EXCL07	Deviation from exclusion criterion 7	Yes
EXCL20	Deviation from exclusion criterion 20	Yes
EXCL21	Deviation from exclusion criterion 21	Yes
EXCL22	Deviation from exclusion criterion 22	Yes
COMD01	Use of prohibited medication during the study	Yes ( from this visit onwards)
WITHO1	Patient who met withdrawal criteria but were not withdrawn	Yes (from the visit subjects met withdrawal criteria onwards)

If updates to this table are needed, an amendment to the SAP will be implemented prior to DBL.

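### FEV1 and ACQ are to be analysed by treatment received, so any treatment mismatch takes the efficacy comparison off the randomised arms, and no arm is defined for a patient given both treatments

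*Protocol*

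**What the plan says.** Protocol 11.1 gives one rule for assigning patients to arms: "For all analysis sets, subjects will be analyzed according to the study treatment(s) received". SAP 4 opens with the same rule, before it defines the sets for safety, PK and PD: "For subjects for which the actual treatment received does not match the randomized treatment the treatment actually received will be used for the analysis". Protocol and SAP agree, and neither makes an exception for efficacy.

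The PD set is the efficacy set. SAP 4 defines it as "all subjects with any available PD data and experienced no protocol deviations with relevant impact on PD or efficacy data" and adds that, after an asthma exacerbation adverse event, "all subsequent efficacy assessments will be excluded from the PD analysis set". SAP 6 treats efficacy and PD parameters together. The rule therefore reaches the primary endpoint in Protocol 2.1 ("Change from baseline FEV1 in mL") and the asthma-control endpoints in Protocol 2.2 ("Change from baseline in ACQ score, % of patients with ≥ 0.5 decrease in ACQ score").

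The visible text contains no efficacy set analysed by randomised arm, no as-randomised sensitivity analysis, and no rule for a patient who receives kits from both arms. Parts of Protocol 11.1 and 11.4 and of SAP 6 are blacked out.

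**The concern.** Treatment received is the usual basis for safety and PK. For efficacy it gives up what randomisation provides. Protocol 3.2 justifies the randomised, blinded design by rigour and by limiting bias, and only a comparison of the groups as randomised keeps that protection when treatment and assignment differ.

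The rule is also incomplete. Protocol 3.3 plans nine dosing occasions per patient. If one kit comes from the other arm, the patient has received both treatments and the rule does not give an arm. Protocol 9.5 expects treatment errors and has them recorded on the dose administration form, but SAP Table 4-1 has no deviation code for a wrong kit. SAP 6.2 provides a blinded case-by-case decision for missed doses only. SAP 1.4 plans at least two interim analyses, at which Protocol 6.4 allows the statistician and other sponsor staff to see individual treatment codes. A decision on the arm that is left open could therefore be made by someone who knows the codes.

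**Working it through.** The plan gives no figure on this point, and its sample-size basis (Protocol 11.7) is blacked out, so there is nothing to reproduce. The calculation below only sizes what a mismatch could do.

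**Inputs**
- Total size, Protocol 3.1: "This study will enroll approximately 110 patients".
- Allocation, Protocol synopsis: "patients will be randomized 3:2 to CJM112:placebo". This gives 110 × 3/5 = 66 and 110 × 2/5 = 44.
- SD of FEV1 change: not visible in either document. I take SE × √n from the placebo groups in SAP Table 10-1, which is an assumption.

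| Study in Table 10-1 | n | SE (L) | SE × √n (L) |
|---|---|---|---|
| AIN457D2204 | 7 | 0.098 | 0.259 |
| QBX258X2201 | 9 | 0.116 | 0.348 |
| QAW029A2206 | 136 | 0.039 | 0.455 |
| QAW039A2214 | 93 | 0.029 | 0.280 |
| Dupilumab trial | 71 | 0.040 | 0.337 |
| Brodalumab trial | 76 | 0.036 | 0.314 |

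Pooled SD = √[Σ(n−1)SD² / Σ(n−1)] = 0.366 L, with a range across studies of 0.259 to 0.455 L.

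**Standard error of the difference.** 0.366 × √(1/66 + 1/44) = 0.366 × 0.1946 = 0.071 L, or about 71 mL.

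**Shift from reassignment.** Assume no drug effect. Let m placebo-randomised patients be counted wholly as CJM112, with a mean d SD from the placebo-arm mean. Then

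shift = SD × d × [m/(66+m) + m/(44−m)].

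For m = 1 and d = 1: 0.366 × (1/67 + 1/43) = 0.366 × 0.0382 = 14 mL. This is 10 to 17 mL over the SD range, and 14/71 ≈ 0.20 standard errors.

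| m | d = 1 | d = 0.5 | d = 0 |
|---|---|---|---|
| 1 | 14 mL | 7 mL | 0 |
| 2 | 28 mL | 14 mL | 0 |

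The sign follows the patient's prognosis. A placebo patient below the mean shifts the result against CJM112, and one above the mean shifts it in favour. With m = 0 the shift is zero.

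**Cost of analysing by randomised arm.** If m placebo patients really receive CJM112 throughout, a true effect is multiplied by 1 − m/44. This is 0.977 for one patient, 0.955 for two and 0.909 for four, or about 2% per patient.

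**Can a kit-error rate supply m?** There are 110 × 9 = 990 administrations. At an assumed error rate r per administration, the expected number of patients with at least one wrong kit is 110 × [1 − (1−r)⁹]: about 1.0 at 0.1% and 4.9 at 0.5%. The documents give no such rate. This number is also not m. Under the same independent-error model, the chance that a patient gets five or more wrong kits of nine at 0.5% is about 126 × 0.005⁵ ≈ 4 × 10⁻¹⁰. The count shows how many patients might meet the mixed-exposure gap, not how many would change arm.

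**The case against.** The strongest case on the other side is that the practical effect is probably nil. Kits are patient-specific and double-blind (Table 6-1), assigned through the IRT (Protocol 6.3) and identical in appearance (Protocol 6.4). Nothing in the documents ties a dispensing error to prognosis, so the expected selection bias may be zero. In an exploratory, non-confirmatory study, a sponsor may also prefer an undiluted estimate by treatment received. The plan has some routes for handling errors: they are recorded, the PD set can drop patients with relevant deviations, and SAP 4 allows Table 4-1 to be amended before database lock. An as-randomised sensitivity analysis may also sit in the blacked-out text.

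Most of this stands as a limit on size, but it does not remove the point. The wording for all analysis sets leaves no room for a set analysed by randomised arm. The existing routes also do not say which arm a mixed-exposure patient belongs to.

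A reader might infer three stronger things that the documents do not support:
- **The randomised comparison is broken as planned.** It is affected only if a mismatch occurs.
- **Plausible kit-error rates imply a bias of tens of mL.** One wrong kit in nine is not a change of arm, and the 1 SD displacement is an assumption.
- **The change has no downside.** It dilutes a true effect when patients really cross over.

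**Conclusion.** The point holds as a conditional defect in the analysis rule. Any mismatch would move the FEV1 and ACQ comparisons off the randomised arms, and mixed exposure has no defined arm. The likely size is small: about 14 mL, or 0.2 standard errors, for one wholly reassigned placebo patient at 1 SD. That figure rests on a 66:44 split, an SD derived from Table 10-1, full reassignment and an assumed link with prognosis. Without that link the expected bias is zero. The reason to act is that the arm rule should be settled before any error is known. The non-confirmatory status lowers the stakes but does not make treatment received the right basis for efficacy.

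**What to change.** In Protocol 11.1 and SAP 4, state that the PD/efficacy set is analysed by randomised treatment and the safety and PK sets by treatment received. Add a rule, fixed before any unblinding (including for an interim analysis), for the arm in which a patient with kits from both arms appears in the as-treated tables. If any mismatch occurs, give the as-treated efficacy result as a supportive analysis, which also covers the dilution.

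The cost is a few sentences in the two documents, with no new data or patients. This is a cheap improvement rather than a free one, because of the dilution of about 2% per fully crossed placebo patient. It does not by itself give a full comparison of everyone randomised: the PD set would still drop patients with listed deviations and all efficacy data after an exacerbation, which needs separate treatment.
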